### **Specific Procedures:**

In phase 2, all eligible participants will receive iTAB-CV. After providing informed consent, all participants will undergo screening followed by a 30-day run-in period in which adherence will be measured using eCAP and self-report. During the 30-day run-in period, participants will continue to receive care as usual and serve as their own control with no intervention. Participants will be provided with the eCAP device for the antihypertensive agent that is missed most often. In the case of more than one such agent, the antihypertensive dosed most often. If there is again more than one such agent, the most recently prescribed agent will be chosen. Based on our experience with MEMs, the Hawthorne effect wears off after 1-2 weeks. After the 30-day run-in period, participants will receive 30 days of stage one of iTAB-CV. The study PI or study staff will conduct an interview in order to customize iTAB-CV for each participant at the baseline session.

In stage one of iTAB-CV, participants begin receiving 1 daily educational/motivational customized text messages addressing medication attitudes, social influences, and self-efficacy which will alternate between antihypertensives and BD medications without reminders and 1 daily mood rating. Participants will identify any stems that they don't want to receive and can write in their own personalized messages. At the 8 week meeting, the study PI or study staff will conduct a brief 2nd iTAB-CV interview to determine the types of medications taken (antihypertensives and/or bipolar medications) and at which times of day as well as to pick reminders/reinforcement texts that the participant wants to receive for stage two.

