### **iTAB-CV:**

At the initial visit we will gather the following information to personalize electronic reminders about medications according to the following steps:

- 1) Identify medications: At the initial assessment we will identify the type of medications taken by each participant at what time of day (participants will be asked to bring all medications to their initial appointment) for hypertension and bipolar disorder. For tracking and reminders, we will identify regularly prescribed medicines for hypertension and bipolar disorder.
- 2) Create categorical description of medications: We will not refer to a specific medication name but rather a medication category (antihypertensive versus bipolar medication) ask participants what name they would like to use to describe this category. We considered using a code name for all participants but those in the 3 patient focus groups indicated that they preferred to use the actual disorder names. Given that it is possible that particular participants may find the name of the disorder stigmatizing, they will have the option to pick their own title to refer to the disorder such as unrelated initials.
- 3) Create personalized reminders: Participants will create their own personalized reminders and remove stems that they don't like. For example, persons may choose to say: "Remember to take ...", or "Your health is important, take..." We will provide a menu of reminder options for participants and they will mark those that they don't want to receive. In order to decrease the tendency to ignore a consistent reminder, the program will be automated to randomly choose and deliver one of the reminder stems created by the participant.
- 4) Identify ideal time for reminders: We will work with participants to identify the best time to send the reminders in order to comply with prescription recommendations. Reminders will be customized for each medication or group of medications. We will also make note of times that participants don't want to receive texts (before or after a certain time of day).
- 5) Confirm receipt of message: Participants will be asked to confirm receipt of their message.

A final personalized example of the reminder might be: "Your health is important, remember to take your HTN medication. Please reply 1 to confirm receipt of this message."

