We will also send text messages once a week that reinforce good adherence to responding to text messages to keep participants engaged (e.g., "Great job responding to all the messages this week!") (See Appendix #3

for sample texts). If they did not respond, they will be encouraged to do so moving forward (e.g. “We really want to hear from you; we hope you will respond to your messages next week!”).

**Electronic Reminder Device:** We will provide participants with mobile devices and we will purchase bulk ‘minutes’ in order to provide the text message intervention. Importantly, participants will not be responsible should they lose or break the device. Participants may use the device for other purposes (e.g., phone calls, calendar functions) as they wish. Participants along with research staff will collaboratively identify a time during the day in which the reminders will occur. Once enrolled in the study, participants will receive full compensation even if they miss all reminders.

**Psychoeducation and training to use electronic device:** All participants will receive a standardized brief psychoeducational presentation with information about hypertension and bipolar disorder as well as training on how to use the electronic device at the 4 week visit.

Participants will respond to a daily mood rating text once a day at the end of the day. Indication of severe low or high moods will trigger an automated text that will direct the participant to go to the ER in case of emergency. After 3 such texts, the system will automatically notify study staff who will follow up with the participant with a phone call.

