The study requires that participants receive medication reminders to take medications as well as answer daily questions about their mood on their mobile device. If a participant chooses to store personal information on this device, it is possible that if the device were lost, the confidentiality of the participant may be compromised. It is possible that participants could put personal information on the device that could link to the delivered text messages, but the risk of losing confidential information in this way is exactly the same as the risk incurred by owning and using any cellular phone. The text messages used in this study are not specific to bipolar disorder and are purposefully generic. Reminders do not use medication names but rather category of medication (high blood pressure medicine or bipolar medicine) and the mood question is generic. While participants in the patient focus groups indicated that they prefer to have the text messages use the actual name or their disorder, participants will have the option of choosing an alternative name if they wish. The text messages will be delivered from a generic phone number that will not be linked to the specific study goals.

If the phone were to be lost, persons could find responses to medication and mood queries. This will be clearly articulated to participants as a study risk and is specified in the consent document. If participants are uncomfortable with this risk, they may choose not to enroll in the study.

Participants will have their blood pressure taken 4 times over a 12-week period. There is minimal risk to blood pressure readings.

The study requires the participant to place a device on top of a standard pill bottle which may compromise the use of pill organizers or other devices to manage their medications. This may affect their medication adherence.

Participants may choose not participate in the study and this will not in any way affect their regular care with clinicians. Individuals who do choose to participate in the study will continue to receive treatment as usual from their regular care provider(s).

It is possible that the subjects' physical or mental health may worsen during their participation. Subjects will be in close communication with the research study team to make sure they are monitored for unexpected worsening and that the appropriate measures are taken.

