**Data security:**

Research files are not available to any unauthorized person. Research data are collected and stored using UH REDCap. Any paper assessment forms are stored in file cabinets in the locked research offices of the PI on the 7th floor of the W.O. Walker Center at [name]. The list that links study ID codes with subject names and all forms bearing subject names will be stored in a password protected file in a folder only accessible to research team personnel on the secure UH server and/or REDCap. Data analysis files will also be stored in the secure folder on the UH network.

Data Safety and Monitoring will be the responsibility of 1) The study's principal investigator ([name]), 2) The local Institutional Review Board (IRB), and 3) a DSMB.

With regard to loss of confidentiality associated with the mobile device, no personally identifying information will be texted by the study team or stored on the device unless the participant chooses to do so. Therefore, if a device is misplaced, there is minimal likelihood that any loss of confidential information will occur.

Adverse events will be assessed and recorded at every visit following the Screening visit. Assessments will include observations by investigators, spontaneous reporting by subjects, and standard non-leading questions. For every adverse event, the PI will provide an assessment of the severity, duration and causal relationship to study intervention, and document all actions taken with regard to study intervention, as well as any other treatment measures for the adverse event. If an outcome for an adverse event is not available at the time of initial report, follow-up will proceed until the outcome is known.

For the purposes of this investigation, a serious adverse event will be defined as any untoward medical occurrence believed to be possibly or probably due to the study and:

1. Results in death
2. Is life threatening
3. Results in persistent or significant disability
4. Is a congenital anomaly
5. Is an important medical event that may not be immediately life threatening or results in death or hospitalization

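### The risk section calls the texts generic and not specific to bipolar disorder, but the plan's own message content is partly about bipolar medication, so the lost-phone risk is understated and inconsistently described

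*Combined protocol and SAP*

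**What the plan says.** All references are to the combined protocol and SAP.

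- **Risks associated with study participation**, on message content: "The text messages used in this study are not specific to bipolar disorder and are purposefully generic". The sentence that follows begins: "Reminders do not use medication names but rather category of medication (high blood pressure medicine or bipolar medicine").
- **iTAB-CV, step 2**, sets the same category: "a medication category (antihypertensive versus bipolar medication"). It reports that one code name for everybody was considered, but that members of the patient focus groups "indicated that they preferred to use the actual disorder names". Staff ask each participant what to call the category. Because the disorder name may be felt as stigmatizing, a participant may choose another title, such as initials that have nothing to do with the illness.
- **Specific Procedures**, on stage 1: 30 days with one educational or motivational text a day, "which will alternate between antihypertensives and BD medications without reminders", plus one mood rating a day.
- **Electronic Reminder Device** (under iTAB-CV): the study supplies the phone, and "Participants may use the device for other purposes (e.g., phone calls, calendar functions) as they wish".
- **Risks associated with study participation**, on a lost phone: a finder could see the participant's answers about medication and mood. The section says that this is explained to participants and set out in the consent document.
- **Data security**: the team texts nothing that identifies the person, and nothing of that kind is on the device unless the participant puts it there. It concludes that "if a device is misplaced, there is minimal likelihood that any loss of confidential information will occur".

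**The concern.** The description of the texts as generic does not survive the sentence after it. A reminder that refers to bipolar medicine is specific to bipolar disorder, even though it names no drug.

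The assessment in Data security has a related gap. It considers identifiers sent by the team and does not consider what the messages say. A message needs no name in it to disclose a diagnosis if the phone that carries it can be tied to its owner, and the plan lets the owner use the phone for calls and calendar entries. The plan also foresees lost phones, since it says that participants are not held responsible for losing one.

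At stake is the disclosure of a psychiatric diagnosis and of daily mood replies. The study's risks are otherwise mainly discomfort with questions and annoyance at texts, so this one should be described accurately. The label is also a choice that the participant makes, and a sound choice needs a correct account of what a finder could read.

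**Working it through.** The point rests on comparing statements. The plan gives no figure for this risk, so there is none to reproduce.

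**1. Are the texts generic as to disorder?**
The risk section says that they are. The same section lists bipolar medicine as one of two reminder categories, and iTAB-CV step 2 defines the categories in the same way. These statements cannot all hold for a participant who keeps the disorder name. The mood question is described as generic, and nothing contradicts that.

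**2. How much of stage 1 concerns bipolar medication?**
Inputs from Specific Procedures: 30 days, one educational text a day, alternating between the two drug classes, and one mood rating a day.
- Educational texts: 30 × 1 = 30.
- On bipolar medication, with strict alternation: 30 / 2 = 15, which is 50% of the educational texts.
- With the 30 daily mood prompts in the denominator: 15 / (30 + 30) = 25%.

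These are shares by topic. How many of the 15 would contain the word bipolar is unknown, because the sample texts in the appendix are not in the material reviewed, and participants may strike out stems or write their own messages.

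**3. Does the Data security conclusion follow?**
Its premise is that no identifying information is texted or stored unless the participant chooses to store it. Three things in the plan bear on the conclusion:
- The risk section says that a finder could see answers about medication and mood. Those are confidential, so the conclusion conflicts with this admission.
- Personal use of the phone is allowed, so the exception in the premise describes a use that the plan itself invites.
- The risk section accepts that personal information on the device could be linked to the study texts.

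The conclusion therefore covers one route to disclosure and is worded as if it covered all of them.

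**4. Is the disclosure in the risk section complete?**
It speaks of the participant's responses being found. It does not say that incoming messages may refer to bipolar medicine.

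**5. Which protections are already described?**
The participant is asked for the label and may choose a neutral one. Drug names are not used. The mood question is generic. The sender number is not linked to the study's goals. Participants may remove stems and may block out times of day. The training at week 4 covers use of the device, but its description does not mention a screen lock.

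**The case against.** The strongest reply is that this is one badly worded sentence in a section that otherwise deals with the risk openly. The plan raises stigma itself, asks each participant which label to use, offers an alternative, avoids drug names, uses a generic sender number, and states that the lost-phone risk is in the consent document. The remark that the risk is the same as with any cell phone is limited to information that the participant stores on the device. The use of disorder names was a patient-informed choice, made after a code name had been considered.

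Most of this stands, and it limits the point. Four stronger readings are tempting, and the documents do not support them:

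- *That nothing protects the participant apart from the optional label.* The protections listed in the working contradict this.
- *That participants consent on a false description.* The consent pages were not available, and the protocol says that they cover the lost phone. Whether they repeat the error is unknown.
- *That a neutral label must be the default.* That would reverse a documented preference of patients. It is a trade-off, and the inconsistency does not settle it.
- *That a count of messages on the handset measures the risk.* The documents give no rate of phone loss and no share of participants who keep the disorder name, and stage-2 reminders mix both drug classes.

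What the reply does not remove is the conflict between the generic description and the reminder category, or the conflict between Data security and the risk section.

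**Conclusion.** The concern holds as a matter of accuracy and participant protection. The statement that the texts are not specific to bipolar disorder is contradicted by the next sentence, by iTAB-CV step 2 and by the stage-1 schedule. The reassurance in Data security is too broad and conflicts with what the risk section admits. The risk is understated and inconsistently described; it is not omitted.

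The only size that the documents support is the topic share: about 15 of 30 stage-1 educational texts, assuming strict alternation over the 30 days and no stems removed. The probability of disclosure cannot be estimated. Disclosure is also not certain for a participant who loses the phone, because it depends on the label chosen, on whether messages are still on the device, and on whether the phone can be tied to its owner.

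Nothing here affects the endpoints, the sample size or the analysis.

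**What to change.** 1. **Risks associated with study participation** and **Data security**: replace the two statements. Say that texts may name the disorder unless the participant picks another label, and that a lost phone can show diagnosis-related messages and mood replies. Check the consent text against this and change it only if it repeats the error.
2. **iTAB-CV, step 2**: keep the participant's choice of label, and explain the lost-phone risk before the choice is made.
3. **Psychoeducation and training to use electronic device**: add setting a screen lock to the existing week-4 session.

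The cost is a few sentences of protocol text, a minute or two at a visit that already takes place, and an occasional forgotten passcode. No assessment, endpoint or analysis changes.

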**Potential benefits associated with study participation:**

It is the goal of this project to contribute knowledge regarding adherence attitudes and effective interventions to improve treatment adherence. It will be explained to subjects that their participation in the study may not benefit them directly. Participants may benefit from participation (e.g. improved symptoms). The iTAB-CV intervention is hypothesized to improve adherence, lower systolic blood pressure and decrease psychiatric symptoms.

**Alternatives to Study Participation**

While participating in this study subjects will continue to receive their usual treatment, including medication prescriptions from their regular mental healthcare provider. Therefore, the alternative to participating in this study is to not participate.

**Compensation for research participation:**

To help cover their costs and reimburse them for their time and effort, each subject will be compensated \$40 for the screening visit and \$30 for each of the remaining three assessments: baseline (4 weeks), visit 1 (8 weeks), and visit 2 (12 weeks). Additionally, participants will receive \$10 for bringing the eCAP to each of the baseline, 8 week, and 12 week visits. Participants will be given bus or parking passes with approximately a \$5 value for transportation for each assessment if needed. Each participant for phase 2 will potentially receive a total of \$160 plus \$20 for transportation if needed. Participants will either be paid by a check mailed to them or petty cash. Transportation reimbursement will be given in the form of a bus pass, a parking voucher, or in rare cases, cash at the time of the visit. Participants will also be able to keep the cell phones provided to them at baseline and unlimited texting from baseline until their completion in the study.

**Cost to participants:**

Participants and their insurance will not be charged for any study visits, phones and free texting are provided for the duration of the study. Subjects may incur costs such as travel, parking, and meals. These are reasonable costs that a subject will incur as a result of going to study visits. Subjects are compensated for these costs as outlined above.

**Compensation for research-related injury:**

If injury occurs as a result of a subject's involvement in this research, medical treatment is available from University Hospitals or another medical facility but the subject or their medical insurance will be responsible for the cost of this treatment. There are no plans for payment of medical expenses or other payments, including lost wages, for any research related injury.

**Plan for Obtaining Informed Consent:**

There will be three layers built into the consent process.

First, all providers and research personnel will be prescreening patients for capacity to give consent – assessing both static factors (e.g. comorbid diagnoses such as intellectual disability) and dynamic factors (e.g. acute psychopathology). Those who are deemed permanently unable to give informed consent will be excluded from studies. Clinicians will be instructed to defer referral of those with severe acute symptomatology until the patient is able to consent, i.e., severe mania accompanied by psychotic thinking.

The second layer is an informal evaluation by study staff of the individual's capacity to give consent to participate. Individuals who are deemed capable of giving informed consent then proceed with screening and enrollment. An authorized member of the investigational staff will explain to potential subjects the aims, methods, reasonably anticipated benefits, and potential hazards of the study, and any discomfort participation in the study may entail. Subjects will be informed that their participation is voluntary and that they may withdraw consent to participate at any time. They will be informed that choosing not to participate will not affect the care they will receive for the treatment of their disease. Subjects will be told that alternative treatments are available if they refuse to take part and that such refusal will not prejudice any possible future treatment. The subject will be given sufficient time to read the informed consent form and the opportunity to ask questions.

Potential participants are provided with the written copy of the consent form with HIPAA language, which they are asked to read and review fully. Following this, the researcher asks whether the participant has any questions and then orally summarizes all the points covered in the informed consent, again inquiring if there are any questions. Prospective participants will be asked to explain what the study will involve in their own words to confirm their understanding. At this point, the third layer is employed by asking subjects questions relevant to the content of the consent form to make sure they have retained vital information and know what they are consenting to participate in (see attached consent quiz). If the subject agrees to participate, the researcher and subject sign the consent form prior to participation. A copy of the signed and witnessed consent form will be given to each subject. The research assistant will then record in the medical record that the consent was obtained and that the decision to participate in the research was "informed".

Due to the nature of bipolar disorder, a patient may be considered "impaired" in decision making capacity due to mania or depression, not due to cognitive impairment. These individuals may be deemed "legally incompetent" and may have a court appointed legal guardian under the statutes of the State of Ohio. If a patient with a legal guardian meets the study's inclusion criteria, the investigator will discuss the study with both the patient and the legal guardian. After obtaining proof of guardianship, both parties will be asked to consent to the patient's participation. If either the patient or the guardian declines to participate, the patient will not be enrolled in this study.

The person obtaining consent will complete the Consent Process document and will file it with the signed consent form in a secure file cabinet separate from the participant's study documents

